In our study in pregnant patients, 1 gram intravenous TXA (or placebo) will be administered immediately after delivery of the infant and after clamping of the umbilical cord to avoid any potential fetal effects. The drug will be prepared and ready to hang at the beginning of the case.

Drug preparation will include the following: Removal of 20 ml from a 50 ml bag of D5W and injection of 10 milliliters of 100mg/ml TXA resulting in a final total volume of 40 ml. Placebo will be prepared by removing 10 ml from a 50 ml bag of D5W. The final volume of the study drug and the placebo bags will be the same and identical in appearance.

Anesthesia staff (physicians and nurse anesthetists) working in the trauma operating rooms will have an in-service about the research study and procedures at a weekly staff meeting to ensure proper education and compliance with study protocol. Intravenous TXA or placebo will be given to the randomized patients by CRMC anesthesia staff after the cord has been clamped and cut based on the intraoperative findings.

All patients undergoing cesarean at high risk for accreta at CRMC have two large bore IVs placed preoperatively. The patient will not require an additional IV for the study drug. TXA is delivered in 5% dextrose plain water and this can be hung as a piggyback with the patient's intraoperative fluids. TXA is clear and colorless and will be visually indistinguishable from the placebo. The hospital pharmacy will be able to provide the placebo.

Primary outcome: The primary endpoint will be estimated intraoperative blood loss (EBL), which is routinely recorded at the end of all operative cases. EBL is *estimated* by the operating room team following a discussion between the surgeon and anesthesia staff based on number of tapes / sponges used, amount of fluid in suction canister, amount of blood on the floor, etc. Secondary endpoints will include amount of blood transfusion, preop and post operative hemoglobin levels, length of hospital stay, ICU admission rates and length of stay, and post-operative complications (DVT, PE, surgical site infection). Maternal demographic information, medical comorbidities, and infant outcomes (weight, Apgar scores, NICU admission) will also be recorded with chart review.

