The pilot trial is planned to last 24-36 months with possible extension if needed to meet study enrollment targets. All final results from the study will be submitted for publication in recognized peer-reviewed obstetrical journals. After completion of the pilot study, a future goal is to approach the Maternal Fetal Medicine Unit Network (MFMU) to organize a larger multi-center trial with additional academic centers (https://www.nichd.nih.gov/research/supported/Pages/mfmu.aspx). The MFMU is a national network established by the NIH to reduce maternal, fetal, and infant morbidity, and to provide the rationale for evidence-based, cost-effective obstetric practice.

Sample Size Calculation

Sample Size: Given the low incidence of placenta accreta at CRMC (approximately 10-15 cases per year), we propose performing a pilot / feasibility study that will include approximately 40 cases over the study period of 3 years. Prior studies using TA in elective cesarean deliveries and post-partum hemorrhage found a 30-33% reduction in estimated blood loss (9, 12). A power analysis with a conservative estimate of 25% reduction in predicted blood loss constraining type I errors to 95% and type II errors to 50% requires 29 patients in each sample given our known average and standard deviation of blood loss in accreta patients from the past year.

Statistical Analysis: Categorical data will be compared using the Chi-square test. Continuous variables, such as estimated blood loss, will be analyzed by comparing means using the Student t-test.

Adverse Events Monitoring (and explanation of routine patient care)

The principle investigator [name] does not typically scrub on planned cesarean hysterectomy cases. These surgeries are typically performed by UCSF faculty sub-specialists, [name] (oncology) or [name] [name] (Urogynecology). However, a coinvestigator (UCSF

resident) will be present in the operating room for all cases, and directly involved in patient care throughout the patient's hospitalization.

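### The only power figure (50% at 29 per arm) is not for the planned enrolment of about 40, and it treats a one-year mean and SD of blood loss as known; at about 20 per arm the implied power is about 36%, with a wide range.

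*Combined protocol and SAP*

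**What the plan says.** All of the sizing argument is in the Sample Size Calculation section. It opens with feasibility: "Given the low incidence of placenta accreta at CRMC (approximately 10-15 cases per year") is the reason given for a pilot of "approximately 40 cases over the study period of 3 years". It then reports a power analysis for a 25% reduction in blood loss, "constraining type I errors to 95% and type II errors to 50% requires 29 patients in each sample". The only description of the planning values behind that number is that it was reached "given our known average and standard deviation of blood loss in accreta patients from the past year". The mean, the SD and the number of women behind them are not given, and nothing allows for their uncertainty. No power is stated for about 40 women.

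Two other places bear on this. The Primary outcome paragraph describes EBL as a measure "which is routinely recorded at the end of all operative cases". The paragraph on trial duration, just before the sample size section, allows 24-36 months "with possible extension if needed to meet study enrollment targets". The Statistical Analysis paragraph specifies a Student t-test on mean EBL.

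**The concern.** Two things are wrong with the stated power. First, it belongs to a trial of 2 × 29 = 58 women, while the plan is for about 40. A reader who takes 50% as this trial's power is misled, and the paragraph offers no other figure.

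Second, the calculation takes the planning mean and SD as fixed quantities. At 10-15 cases a year, one year of patients is a very small sample from which to estimate a variance, so even a correctly matched power figure would carry a large error that the plan does not show.

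What is at stake is how the result is read. The Hypothesis section aims to show a 25% reduction. If the trial finds no significant difference, its weight as evidence depends on the power it really had. The test, the endpoint and the randomization are not in question here.

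**Working it through.** **Inputs.** From the documents: 29 per arm, type II error 50%, 25% relative reduction, equal allocation, Student t-test, about 40 women planned, 10-15 cases a year. Assumed: the type I statement means 95% confidence, so alpha is 0.05, two-sided; EBL is roughly normal for the interval on the CV; the planning sample is 10 or 15 women.

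**Step 1. Back-solve the plan's figure.** It cannot be reproduced directly because the mean and SD are not given. With a difference of 0.25 × mean, the standardized effect is d = 0.25 / CV, where CV = SD / mean. The power of the t-test with n per arm comes from a noncentral t with 2n − 2 degrees of freedom and noncentrality d × √(n/2).

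- n = 29: 56 df, critical value 2.003. Power of 0.50 needs a noncentrality of 1.994, so d = 1.994 / √14.5 = 0.524.
- CV = 0.25 / 0.524 = 0.477.
- The normal approximation gives CV 0.486, and a CV of 0.48 returns 29 per arm. The plan's figure is therefore internally possible.

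**Step 2. Power at the planned size.** For n = 20: noncentrality = 0.524 × √10 = 1.656, 38 df, critical value 2.024. Power = 0.365, or about 36%.

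**Step 3. Uncertainty in the CV.** With m planning women, √m / (observed CV) follows a noncentral t with m − 1 df and noncentrality √m / (true CV). Inverting this gives an exact 95% interval under normality. For m = 10: √10 / 0.477 = 6.62; the noncentrality limits are 2.98 and 10.16; the CV limits are 3.162 / 10.16 = 0.311 and 3.162 / 2.98 = 1.06. Each limit goes back into d = 0.25 / CV and the power formula.

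| Planning women | 95% interval for CV | Power at 20 per arm | Power at 29 per arm |
|---|---|---|---|
| 10 (one year) | 0.311-1.060 | 11-70% | 14-85% |
| 15 (one year) | 0.333-0.859 | 15-64% | 19-80% |
| 50 (five years at 10) | 0.386-0.628 | 23-51% | 32-68% |
| 75 (five years at 15) | 0.400-0.593 | 26-49% | 35-65% |

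**Step 4. Sensitivity to the assumptions.**

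- One-sided 0.05: CV 0.572; power at 29 per arm 17-82% (10 women) or 22-78% (15 women).
- Lognormal EBL: 15-82% or 20-77% at 29 per arm.
- Only the SD uncertain, mean taken as exact: 19-81% or 24-76% at 29 per arm.
- Larger planning group: if 10-15 counts confirmed cases only, and the planning group was all suspected women at 40-60% risk, it held about 10 / 0.6 = 17 to 15 / 0.4 = 38 women. Power at 20 per arm is then 16-62% (17 women) or 22-54% (38 women).

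The range narrows in some variants, but none comes close to supporting a single figure.

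**The case against.** The strongest reply is that the SD does not decide this trial's size. Enrolment of about 40 is set by incidence: 10-15 cases a year for 3 years is 30-45 women. The study is called a pilot, and a 50% type II error already admits low power. Better planning data would leave it underpowered, with the same test and endpoint. This stands, and it limits the point to a correction of a stated figure. It does not rescue that figure, because the admitted 50% belongs to 58 women.

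The number of planning women is also an inference from annual incidence. That stands, and is one reason to ask for the number. Routine recording of EBL makes earlier data likely, but the documents do not say that older records are retrievable or comparable. The Standard of Care paragraph shows that balloon placement depends on surgeon preference, and the Background says incidence is rising, so five past years may hold fewer than 50-75 women.

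A reader might infer more than the documents support, in three ways:

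- **That power could be anywhere from 14% to 85%.** Those are 95% limits at 29 per arm, conditional on the back-solved CV. They are not bounds, and they do not apply to the planned size.
- **That the enrolment target should rise to cover the uncertainty**, for example by sizing on an upper confidence limit of the SD. That is a debatable convention, and 58 women would already take 58 / 15 = 3.9 to 58 / 10 = 5.8 years. The extension clause does not say that 29 per arm is one of the targets it refers to.
- **That this SD will go on to size the later study.** The plan only hopes, once the pilot is complete, "to organize a larger multi-center trial with additional academic centers". Nothing says that the past-year SD would be used, and by then about 40 randomized women would supply a pooled SD on about 38 df (95% factor about 0.82-1.29).

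**Conclusion.** The point holds as a correction to the stated power, of modest weight. The plan's one power figure does not apply to its own enrolment, and it rests on planning values presented as known that probably come from 10-15 women. At the planned size the implied power is about 14 points lower, and a 95% range on it spans about 50-60 points.

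This rests on alpha 0.05 two-sided, a t-test on roughly normal EBL, a CV that gives exactly 50% power at 29 per arm, and a planning sample equal to one year's case count. The gap between 50% and about 36% needs only the first three of these; the width of the range needs all four. The documents do not support a claim that the sample size itself is wrong or must change.

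**What to change.** In the Sample Size Calculation section:

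1. Replace the 50% figure with the power for a 25% reduction at about 20 per arm, as a point estimate with a range over the 95% interval of the SD or CV. State alpha and whether the test is one- or two-sided.
2. Report the number of women, mean and SD of EBL behind it, and say whether they were confirmed or suspected cases.
3. Where earlier EBL records are retrievable and reflect comparable practice, pool them with the past year and recompute. If they are not comparable, keep the one year and report its wider range.

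The cost is a few sentences and, for item 3, some chart review, including a check of eligibility against imaging and obstetric history. The stated power becomes less favourable, and older records may bring drift in surgical practice into the SD.

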Drug purchasing: Per CRMC policy, the pharmacy cannot charge a patient for an approved drug in a research protocol. However, the CRMC pharmacy regularly purchases the study drug for use in surgical patients. The CRMC pharmacy has agreed to purchase the study drug for the principle investigator ([name]), and the studies' grant money will be used to reimburse the pharmacy at cost. Each vial of 1 gram of tranexamic acid for intravenous administration costs the pharmacy \$16.70. An initial box of ten vials has been purchased and additional boxes will be ordered after five patients are enrolled.

Randomization protocol: The drug and placebo will be stored, logged, and dispensed from the CRMC Inpatient Pharmacy. A recruited patient will be labeled study subject number one, and so on, by the study investigators. The name and study number will be given to Inpatient Pharmacy. Inpatient Pharmacy staff will randomize the subject to treatment or placebo using a blocked randomization technique and a computer protocol designed with assistance from [name]. The block size will be set at 4-6 to ensure that the number of treatment and placebo subjects are as close to equal as possible. Inpatient Pharmacy will assign that patient to receive drug or placebo prior to the scheduled surgery. The randomization assignments for each study subject will be located in a study binder in the research pharmacy space. Inpatient Pharmacy staff members will be the only unblinded study staff. The study investigators, clinicians, patient, and hospital staff will be blinded to treatment assignments.

Pharmacy and Drug Delivery Protocol:

Drug purchasing: Per hospital pharmacy policy, the study drug must be ordered from an outside pharmacy. The study drug will be purchased by the investigator from a non-CRMC pharmacy using her DEA number and delivered to the research pharmacy technician. The online pharmacy will be accredited with the National Association of Boards of Pharmacy member and recommended by chief hospital pharmacist.

Drug delivery: In orthopedic and cardiac surgery, 1 gram of intravenous TXA is routinely given 15 minutes before incision time. TXA is typically prepared at CRMC by removing 20cc of fluid from a small IV bag of 5% dextrose in plain water and then injecting the drug into the remaining 30 cc. This is then delivered with an IV piggyback with the patient's preoperative fluids.

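### The blanket chi-square rule gives no defined or unambiguous result for sparse complication tables (DVT, PE, infection) at about 20 women per arm

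*Combined protocol and SAP*

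**What the plan says.** The Statistical Analysis paragraph under Sample Size Calculation has one rule for this type of data: "Categorical data will be compared using the Chi-square test". It states no expected-count threshold, exact alternative, choice about continuity correction, effect estimate or confidence interval, and nothing on tables without events.

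The rule reaches the secondary endpoints listed under Methods, Primary outcome. These include ICU admission and "post-operative complications (DVT, PE, surgical site infection"). No expected rate is given for any of them.

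The Sample Size paragraph plans "approximately 40 cases over the study period of 3 years". The Randomization protocol says "The block size will be set at 4-6 to ensure that the number of treatment and placebo subjects are as close to equal as possible". Together these imply about 20 women per arm. The power analysis, which concerns blood loss only, "requires 29 patients in each sample given our known average and standard deviation of blood loss in accreta patients from the past year".

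**The concern.** The chi-square test relies on a large-sample approximation. A rare complication in 40 women gives a table with few events or none. The stated rule then fails in one of two ways: it returns no result, or it returns one that depends on whether the software applies a continuity correction by default. Both the corrected and the uncorrected statistic answer to the name chi-square, so the plan leaves the choice open until the data are in hand.

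Thrombosis is the risk that the protocol itself names for this drug (Risks to Human Subjects, Potential Risks), and the results are to be published and used to seek a larger multicentre trial. For that purpose, an estimate with an interval says more about complications than a missing or default-dependent p-value.

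**Working it through.** **The plan's own figure.** The only computed figure is 29 per arm, for blood loss. With power 50% the second normal quantile is zero, so n = 2 × 1.96² × CV² / 0.25², where CV is SD/mean. Setting n = 29 gives CV = √(29 × 0.0625 / 7.683) ≈ 0.49 two-sided (a t-based solution gives about 0.48). The mean and SD are not stated, so 29 cannot be confirmed. It has no bearing on the categorical outcomes except as an alternative arm size, used at the end.

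**Inputs.** n = 20 per arm, from about 40 cases and near-equal allocation. Event risks are assumptions, since the documents give none; the range shown is 1% to 10%, the same in both arms unless stated.

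**Expected counts.** With equal arms, the expected count in each event cell is half the total number of events. A value of 5 needs 10 events in 40 women, or 25% overall. At true risks up to 10%, the chance of falling short of that is at least 99%.

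**Undefined result.** With no event in either arm, the statistic is 0/0. The probability is (1 − p)^40.

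**Default-dependent result.** All 21 × 21 tables were enumerated. Every table significant at 0.05 with the correction is also significant without it, so the chance of disagreement is the difference between the two rejection rates. At 10% risk this is 3.87% − 0.41% ≈ 3.5%.

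| Assumed risk | Expected events per arm | No event in either arm | Corrected and uncorrected disagree |
|---|---|---|---|
| 1% | 0.2 | 67% | below 0.08% |
| 2% | 0.4 | 45% | 0.08% |
| 5% | 1 | 13% | 1.1% |
| 10% | 2 | 1.5% | 3.5% |

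**Two tables worked through.**

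- 4 v 0, uncorrected: 40 × (4 × 20 − 16 × 0)² / (20 × 20 × 4 × 36) = 4.44, p = 0.035. Corrected: 40 × (80 − 20)² / 57,600 = 2.50, p = 0.114. Fisher: 2 × C(20,4) / C(40,4) = 2 × 4,845 / 91,390, p = 0.106.
- 6 v 1, uncorrected: 40 × (6 × 19 − 14 × 1)² / (20 × 20 × 7 × 33) = 4.33, p = 0.037. Corrected: 40 × (100 − 20)² / 92,400 = 2.77, p = 0.096. Fisher: p = 0.091.

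**Type I error.** The uncorrected test's actual rate peaks at about 5.3%, near a risk of 0.3. At a risk of 5% it is about 1.2%.

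**Power.** For 5% v 15%, the chance of p < 0.05 is 15% uncorrected, 3% corrected and 7% with Fisher. Corrected and uncorrected then disagree in about 12% of trials.

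**What an interval would show.** The Wilson upper limit for 0/20 is 1.96² / (20 + 1.96²) = 0.161. The Newcombe interval for 0/20 v 0/20 is therefore about −16 to +16 percentage points. For 1/20 v 0/20 it is about −12 to +24.

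**At 29 per arm.** The pattern is the same. No event occurs in 56% of trials at 1% risk and 31% at 2%, and 4 v 0 gives 0.038, 0.120 and 0.112 (uncorrected, corrected, Fisher).

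**The case against.** The best defence is that this is a pilot whose primary endpoint is continuous and analysed by t-test. Complications are secondary, and safety is handled case by case: under Adverse Events Monitoring, a clot or death goes to the safety monitoring committee within 48 hours. No decision in the plan hangs on a chi-square p-value. An event-free table can simply be reported as zero events, and tables on which software defaults disagree are uncommon when the true risks are equal. All of this stands, and it is why the point is minor. Case review does not, however, supply the between-arm comparison that will be published.

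Four stronger readings are tempting and are not supported.

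- *A non-significant test will be taken as proof of safety.* The documents do not say so. The statement in Potential Risks about no significant increase describes earlier systematic reviews, not a rule for this trial. The misreading is something to guard against, not something planned.
- *Chi-square inflates false positives here.* It does not to any material degree; the maximum is 5.3%.
- *Every categorical outcome is affected.* A common one need not be. At a 40% rate, the expected count falls below 5 in only 1.6% of trials, and ICU admission may be such an outcome.
- *A better test would detect harm.* Low power comes from the sample size; Fisher's test has less power than uncorrected chi-square.

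Nor does the plan limit its output to p-values: the endpoint list itself refers to ICU admission rates. What is missing is a stated effect estimate and interval.

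**Conclusion.** The concern holds as a minor gap in the analysis wording. Followed literally, the rule gives no result for event-free tables, which is likely for DVT or PE if their risks are 1% to 2% (67% and 45% of trials) and unlikely for an outcome at 10% (1.5%). For certain sparse tables it gives a verdict that an unstated software default decides, in at most about 3.5% of trials under equal risks up to 10%, and more often if the risks truly differ.

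These figures rest on about 20 women per arm and on assumed event rates. At 29 per arm the conclusion is unchanged. The blood-loss analysis and the case-level safety review are not touched.

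**What to change.** Replace the sentence on categorical data with wording to this effect:

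- Binary outcomes are reported as counts per arm and a risk difference with a Newcombe (score-type) 95% confidence interval.
- Where any expected cell count is below 5, the test is the two-sided Fisher exact test; otherwise it is Pearson's chi-square without continuity correction.
- Comparisons of DVT, PE and surgical site infection are descriptive. The report notes that even 0/20 v 0/20 is compatible with a difference of about −16 to +16 percentage points, so non-significance is not evidence of no harm.

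Name one exact test only. Boschloo's test would give 0.061 for 4 v 0 and 0.046 for 6 v 1. Allowing either it or Fisher (0.106 and 0.091) would bring back the dependence on software, because 6 v 1 is significant by one and not by the other. The threshold of 5 is a convention; what matters is that it is fixed before the data are seen.

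The cost is a few sentences and trivial programming, with no change to design, recruitment or data collection. There are two downsides. Fisher's test is more conservative (7% v 15% power for 5% v 15%), and the published safety statement becomes less favourable.

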ID: 2016036 Perioperative Administration of Tranexamic Acid for Placenta Previa and Accreta Study

Perioperative Administration of Tranexamic Acid for Placenta Previa and Accreta Study (TAPPAS): A Randomized, Placebo-controlled Double Blind Trial

UCSF Fresno Department of Obstetrics and Gynecology

Brief Synopsis

The purpose of this pilot study is to determine if intravenous tranexamic acid (TXA) is effective for reducing blood loss during high risk surgical procedures related to placenta previa and placenta accreta. TXA is currently used in other types of surgery for patients who are expected to have a large blood loss, such as orthopedic or cardiac surgery. The drug will be given AFTER delivery of the baby, so there is no risk of harm to the infant when participating in the study.

Background

Significance: The incidence of morbidly adherent placenta is rising due to increasing cesarean rates, and is currently estimated at 1 in 500 to 700 deliveries. Placenta accreta, a condition in which the placenta abnormally invades the uterine wall, carries a high risk of operative complications and often requires cesarean hysterectomy. Cesarean hysterectomy leads to higher intraoperative blood loss and morbidity when compared to a routine cesarean delivery. Retrospective reviews estimate there a 40% risk of requiring blood transfusion over ten units, and a 7% risk of maternal death (1).

Placenta accreta can be suspected antenatally based on certain risk factors, such as prior cesarean delivery and abnormal placenta location. For example, a woman with 3-4 prior cesarean deliveries and a placenta previa (low lying placenta) has a 60% risk of placenta accreta (14). Additional ultrasound and/or MRI studies can identify suspicious imaging features. However, diagnosis cannot be confirmed until the time of surgery, at which point abnormal placental behavior (hemorrhage, or failure of the placenta to detach) may be observed. The diagnosis is confirmed by final pathology report. Women with multiple prior cesarean sections, placenta previa, and placenta accreta have greater expected intraoperative blood loss, perioperative complications and morbidity than primary (first-time) cesarean sections (14).

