There has been growing interest in the application of tranexamic acid in obstetrics and gynecology. In multiple international studies, intravenous TXA has been shown to significantly reduce blood loss when given prophylactically with cesarean delivery or vaginal delivery without an increase in morbidity from adverse thrombotic events (6-9). Currently, a large, international (n=15,000) clinical trial is being conducted in middle- and low-income countries investigating the use of TXA for post-partum hemorrhage after vaginal delivery (10). A recent Danish study has also been completed regarding the use of TXA in benign gynecologic surgeries, i.e. routine hysterectomy (11). Furthermore, in March of 2016, Pacheco et al released new guidelines recommending the use of TXA in all obstetrical cases requiring massive transfusion protocol. TXA is recommended to be given in round three of obstetrical hemorrhage cases (1 gram intravenously over 10 minutes). (15). The authors called for more research to clarify the role and timing of administration of the drug in high risk obstetrical populations. Lastly, the 2015 Cochrane review of more than 3,000 obstetrical patients given TXA showed reduction in bleeding with no increase in adverse events including thromboembolism (16).

To date, TXA has not been studied in the particular population of patients requiring cesarean hysterectomy for placenta previa or accreta. This inexpensive, low risk medication has potential to greatly reduce perioperative morbidity and cost when used in a uniquely high risk obstetrical population.

Hypothesis

We predict tranexamic acid will reduce intraoperative bleeding associated with cesarean hysterectomy in patients with suspected placenta accreta compared to placebo. We aim to perform a pilot study showing a 25% reduction in estimated blood loss versus placebo.

Methods

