Study design: This pilot study will be conducted as a randomized, placebo-controlled, double blind trial in the CRMC obstetrical department. The subjects will be recruited from outpatient clinics by the principal investigator or co-investigators during their routine antenatal care. Study consent will be secured during a routine antepartum outpatient visit, or sometimes during an antenatal admission to Labor and Delivery. The majority of patients at CRMC and CCMC with suspected placenta accreta are referred to the perinatologists at the Prenatal Diagnostic Center, and we anticipate most patients will be recruited from this practice. We will not attempt to recruit new patients who are in active labor, or those with medical acuity who require immediate intervention.

Study population: A consequence of studying pregnant women is that all of our study subjects will represent a vulnerable population. Based on our patient demographics, we anticipate a large proportion of the women in our study will be of Hispanic ethnicity, and will be preterm (before 37 weeks gestation). In general, patients with suspected placenta previa have a planned preterm delivery at 34-36 weeks.

Inclusion criteria:

- English and Spanish speaking pregnant

- Any order pregnancy (singleton, twin gestation, etc)

- With a suspected accreta based on ultrasound or MRI imaging studies

- All women evaluated for placenta accreta and deemed to be high risk for this disease (≥40% risk) ^{(14),} meaning women diagnosed with a placenta previa and greater than or equal to 2 prior c-sections

Exclusion criteria:

- Women less than 18 years of age

- Women with a personal history of venous or arterial thrombosis (deep vein thrombosis, pulmonary embolism, myocardial infarction, or stroke

- Women with a personal history of clotting disorder, such as anti-phospholipid syndrome
- Women who do not have a good understanding of either English or Spanish will be excluded.

- Women with defective color vision (color-blindness) [See Appendix A]

Pharmacy and Drug Delivery Protocol:

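### Minor: hemoglobin would be compared by an unadjusted t-test although the pre-operative value is collected; analyse the post-operative level by ANCOVA, and report the EBL effect as a percentage with a 95% CI

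*Combined protocol and SAP*

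**What the plan says.** The analysis plan is two sentences in the Statistical Analysis paragraph under Sample Size Calculation. Categorical data get a chi-square test. For the rest, "Continuous variables, such as estimated blood loss, will be analyzed by comparing means using the Student t-test". No covariate, effect estimate or confidence interval is named.

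The Primary outcome paragraph names estimated intraoperative blood loss (EBL) as the primary endpoint and continues: "Secondary endpoints will include amount of blood transfusion, preop and post operative hemoglobin levels". It does not say whether the post-operative level or the change is to be compared, or what role the pre-operative value has.

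The Hypothesis section puts the aim on a percentage scale: "We aim to perform a pilot study showing a 25% reduction in estimated blood loss versus placebo". The sample size uses the same 25%. It "requires 29 patients in each sample given our known average and standard deviation of blood loss in accreta patients from the past year", but the mean and standard deviation are not printed. Planned enrollment is about 40 women in total.

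**The concern.** Hemoglobin is the one outcome for which the plan already collects a baseline measurement of the same quantity. A t-test on post-operative levels ignores that measurement. A t-test on the change uses it with a fixed coefficient of 1, which adds noise when the correlation is modest. Because the plan names neither, the choice could be made after the data are seen. Listing the pre-operative level as part of an endpoint also leaves room to test it between arms. Any difference found there would reflect chance, because the study drug is given after the cord is clamped.

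For EBL, the trial aims at a percentage reduction, but no percentage estimate or interval is promised. Those figures would be useful for planning the larger multi-center trial that the protocol names as a future goal.

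At stake are precision and clarity in a secondary endpoint, and how informative the primary result is. The validity of the t-test is not in question.

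**Working it through.** **1. Hemoglobin: variance of the treatment comparison**

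Inputs: N = 40 (Sample Size Calculation), taken as 20 per arm. Assumed: equal standard deviations before and after surgery, and a pre/post correlation r from 0 to 0.5. The documents give no value for r.

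Variance relative to a t-test on post-operative levels (= 1):

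- ANCOVA: (1 − r²) × 37/36. The factor 37/36 = 1 + 1/(40 − 4) is the expected cost of chance imbalance in the covariate.
- t-test on change: 2(1 − r).

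| r (assumed) | ANCOVA | Change score |
|---|---|---|
| 0 | 1.03 | 2.0 |
| 0.2 | 0.99 | 1.6 |
| 0.3 | 0.94 | 1.4 |
| 0.4 | 0.86 | 1.2 |
| 0.5 | 0.77 | 1.0 |

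For example, at r = 0.4: (1 − 0.16) × 1.028 = 0.863.

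Break-even with post-operative levels: (1 − r²) × 37/36 = 1, so r² = 1/37 and r = 0.16. ANCOVA has lower variance than the change score at every r in the table.

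**2. EBL: what a percentage with an interval would show**

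The plan's 29 per arm cannot be reproduced directly, because the mean and standard deviation are not printed. It can be back-solved. I read the stated error rates as a two-sided 5% test with 50% power, and assume a common standard deviation. With 29 per arm (56 degrees of freedom, noncentral t), the standardized difference is d = 0.524, so the coefficient of variation is 0.25/0.524 = 0.477.

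Suppose exactly 25% is observed with 20 per arm, in units of the placebo mean:

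- Standard error of the difference: 0.477 × √(2/20) = 0.151.
- t = 0.25/0.151 = 1.66 on 38 degrees of freedom, p = 0.106.
- Mean difference 0.25, 95% CI −0.06 to 0.56.
- Percentage reduction by the delta method on the log ratio of means: standard error 0.477 × √[(1 + 1/0.75²)/20] = 0.178, half-width 0.360. The ratio runs from 0.75·e^(−0.360) = 0.523 to 0.75·e^(0.360) = 1.075, a reduction of about −8% to 48%.

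**3. EBL: would adjusting for prior cesareans help?**

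Under the same back-solved inputs, power at 20 per arm is 36.5% unadjusted. With one covariate the residual variance is (1 − R²) × 37/36 on 37 degrees of freedom. Power is then 35.6% at R² = 0, and equals the unadjusted value at R² = 0.028.

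The only gradient that the documents give within this population is in accreta risk: at least 40% at the entry threshold, and "a woman with 3-4 prior cesarean deliveries and a placenta previa (low lying placenta) has a 60% risk of placenta accreta". Take 40% for exactly 2 prior cesareans and 60% for 3 or 4, with assumed shares of 50/30/20% for 2, 3 and 4:

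- Mean count 2.7, variance 0.61. Overall accreta risk 0.5, variance 0.25. Covariance 0.07.
- R² of the count with accreta status: 0.07²/(0.61 × 0.25) = 0.032. Other share mixes give 0.027 to 0.032.

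This is the ceiling by this route, reached only if accreta explained all EBL variance. If accreta cases bleed D within-group standard deviations more (assumed), the R² for EBL is 0.032 × 0.25D²/(1 + 0.25D²):

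| D (assumed) | R² | Adjusted power |
|---|---|---|
| 0.5 | 0.002 | 35.7% |
| 1 | 0.006 | 35.8% |
| 2 | 0.016 | 36.1% |

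Each is slightly below the unadjusted 36.5%.

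**The case against.** **The hemoglobin gain is assumed.** This stands. The correlation is not in the documents, and the Background cites a "40% risk of requiring blood transfusion over ten units" in accreta, so transfusion may push it down. Below r = 0.16 ANCOVA is slightly worse than comparing post-operative levels. Nor does ANCOVA remove the effect of transfusion on post-operative hemoglobin, and transfusion is itself a secondary endpoint. The loss, however, is capped at about 3% of variance.

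**The plan does not limit the report to a p-value.** This also stands. A comparison of means yields the difference and its interval, and the percentage follows by dividing by the placebo mean. The EBL part is therefore a reporting clarification.

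**Stronger readings that a reader might draw:**

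- *The primary EBL analysis should be adjusted for prior cesareans.* The Background does describe "greater expected intraoperative blood loss, perioperative complications and morbidity than primary (first-time) cesarean sections", but that comparison is with first-time cesareans, not between women who all enter with "greater than or equal to 2 prior c-sections". Inclusion criteria also list imaging suspicion as a separate item without saying whether both must be met, so counts of 0 or 1 may be possible. An R² of 0.1 to 0.2 would raise power to about 39–43%, but nothing in the documents supports such a value.
- *Low power makes this serious.* The low power comes from planning about 40 women against 58 required (2 × 29). That is a separate issue, which neither change here repairs.
- *Unblinding during the study makes pre-specification urgent.* The Adverse Events Monitoring section reveals single assignments after a significant adverse event, and investigators are otherwise blinded. That gives little scope to choose a covariate by its result.

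**Conclusion.** The point holds as a minor one. For hemoglobin, ANCOVA is a better method on data already collected. It settles an undefined comparison and changes the variance by between about 3% more and 23% less than a t-test on post-operative levels, over assumed correlations of 0 to 0.5. It is better than a change-score t-test throughout that range. These figures assume 20 per arm and equal pre- and post-operative standard deviations.

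For EBL, the t-test is valid and can stay. Adding the percentage reduction with its interval matches the result to the 25% aim. The illustrative interval of −8% to 48% rests on a coefficient of variation back-solved from the plan's 29 per arm.

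The documents support no expected power gain from adjusting EBL for prior cesareans, and possibly a loss of under 1 point.

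**What to change.** Add one short paragraph to Statistical Analysis, fixed in writing before the data are analysed:

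- Analyse post-operative hemoglobin by ANCOVA on treatment, with pre-operative hemoglobin as covariate. Do not test pre-operative hemoglobin as an outcome; describe it by arm.
- Keep the Student t-test for EBL. Report the mean difference and the percentage reduction (1 minus the ratio of means), each with a 95% CI, using the delta method or bootstrap for the percentage.
- Leave the number of prior cesareans out of the primary EBL analysis. If it is of interest, name it as an optional sensitivity analysis.

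The cost is the paragraph itself and one degree of freedom in the hemoglobin model, with about 3% more variance if the pre-operative value proves uninformative. No new data are needed. The report should say that post-operative hemoglobin is still affected by transfusion.
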